# 5.2 Analysis populations

The primary analysis will be an intention to treat (ITT) analysis in all participants, separately per study arm. A per protocol (PP) population will be all study subjects completing the study period with a median compliance above or equal to 80% (if sufficient n, e.g. n=30) or alternatively stratifying group by compliance above and beyond the compliance median. Additionally, the effect of compliance to the intervention will be evaluated using linear mixed-effects models with the compliance score as covariate. Timing may be coded as days since baseline rather than categorical variable (M2, M4, M6).

# 5.3 Control group

A control group of women with similar characteristics would have been desirable, yet for practical reasons would have proved challenging. The study constitutes a considerable effort for the participating group of healthy volunteers. Participants in a control group may not have seen a sufficient benefit for their participation and would have likely dropped out at high rates. Moreover, it would have not been possible to include a group of smokers and instruct them to not stop smoking for at least another 6 months. It is furthermore possible that participants in the control arm might have changed their health behaviours as they are increasingly confronted with health as part of the study.

Instead we have opted to utilise a longitudinal baseline-controlled design. Importantly, participants who are non-compliant are not excluded from the study. If they able to continue to provide samples, we include these samples as a type of "nested control" (i.e. what would happen without intervention?). Descriptive statistics of dynamics over 6 months without an intervention will be reported and if sufficient individuals are present per study arm ( $n \ge 10$ ) that did not adhere, these may be used as a nested control group, although this number is small.

# 5.4 Definition of primary, secondary, and subsidiary endpoints

#### 5.4.1 Primary objective

To assess whether a reduction/cessation in risk exposure (smoking, continuous non-timerestricted calorie intake resulting in being overweight/obese) via lifestyle modification over six months results in significant absolute changes in DNA methylation-based disease risk and ageing scores compared to baseline in cervical samples. Scores of the following age signatures will be evaluated:

- signatures that have previously been published, including
  - WID-BC
  - WID-OC
  - WID-EC
  - WID-CIN
  - WID-REA
  - WID-RIA
  - pcgtAge
- signatures that are not yet published but have been developed by the study group
  - Group of markers indicative of (stem) cellular age, e.g. WID-PCGT (general/immune/epithelial),
    WID-SEN (general/immune/epithelial), WID-PRO (general/immune/epithelial),
    etc. thereafter referred to collectively as "WID-SOLA"
- signatures indicative of exposure, e.g.
  - WID-SMK smoking index

Successful completion relates to a significant reduction in two ore more risk scores with no significant in increase in any of the scores.

Analysis will be conducted both ITT, intention to treat, and PP, per protocol, comparing baseline and month 6. ITT analysis may be conducted as a mixed-effects models, using compliance score as a covariate. A per protocol analysis may be conducted either by median compliance rate above or equal to 80%, or alternative split by mean or median compliance rate (see Figure 1).

Subgroup analyses will also be conducted as follows:

- 1. smoking cessation study arm: investigation of the impact of the use of electronic cigarettes on smoking signature scores
- 2. intermittent fasting study arm: investigation of difference between individuals who received ketogenic supplement and those that did not at 6 months
- 3. intermittent fasting study arm: subgroup analysis by fasting pattern (breakfast or dinner skipping)

#### 5.4.2 Secondary objectives

We will describe and report general study characteristics:

#### General study characteristics

• dropout rate

Is the dropout rate consistent with the literature (approximately 15-20% for lifestyle

interventions)? The analysis will be reported separately for the two sub-studies and randomised trial arms.

- *compliance* What is the compliance across the two sub-studies?
- sign-up rate

Out of participants that originally registered interest, how many wanted to finally participate and how many were included after meeting the criteria?

Moreover, the study will describe longitudinal alterations in a variety of health parameters (see also Fig. 2):

#### Molecular endpoints

• epigenetic markers

DNA methylation-based disease risk, ageing, and exposure signatures in cervical, buccal, and blood samples.

- microbiome
  - changes in overall diversity and proportions of certain beneficial or harmful microbial species in fecal microbiome depending on the intervention
  - distinction of health and lean individuals using microbiome
  - distinction of smokers and non-smokers using microbiome
  - shift in dominant types and association with weight loss
  - potential changes in functional prediction
- *metabolites* alterations in metabolic profile of urine and saliva
- blood profile
  - lipids and HbA1c levels
  - cellular markers of inflammation
  - guided by cellular alterations, targeted investigation of levels of inflammatory cytokines and markers in blood plasma
- ageing markers in the skin and skin barrier function

#### Clinical and epidemiological endpoints

- body mass index (BMI), diet arm of the study
- body composition (muscle, fat, water), diet arm of the study
- smoking status, *smoking arm of the study*, including

- current smoking (yes/no)

- cigarettes in the last 7 days
- use of nicotine replacement products
- vascular health

pulse wave velocity, intima-media thickness, and plaque score before and after intervention

- abdominal fat composition, *diet arm of the study* visceral and subcutaneous fat before and after 6 months of intervention
- physical activity and health measured using the international physical activity questionnaire (IPAQ), sports examination (VO2max), and fitness tracker (daily steps, active minutes, floors climbed); resting heart rate
- pulmonary health

#### **Psychological** endpoints

- health-related quality of life (EuroQoL) before and after 6 months of intervention
- psychological self-efficacy before and after 6 months of intervention

#### 5.4.3 Subsidiary outcomes or objectives

Optional samples are collected at month 12 and month 18 after inclusion into the study. Samples may be collected to evaluate long-term stability of changes in those participants that showed epigenetic and other biological changes in response to the intervention:

- ongoing "compliance" to smoking cessation or intermittent fasting: participants are not specifically instructed to continue with any intervention but it will be evaluated how many participants continue to be smoke-free or undergo intermittent fasting. It is likely that individuals that were highly compliant to begin with may be more likely to return for optional follow ups, which will need to be considered for this analysis.
- variability in epigenetic and other health markers evaluated in primary and secondary endpoints at month 6 and month 12 and/or month 18

Additionally, it is a subsidiary objective to identify changes in the following parameters in response to the intervention in subgroups of participants:

- blood (immune) cell identity and composition as assessed via multiomic single cell RNA- and ATAC-seq in a subgroup of patients (pilot study, baseline and 2 months): reduced numbers of inflammatory cell populations, increased chromatin accessibility at PCGT sites.
- epigenetic reprogramming signatures
- characterisation of epigenetic alterations following intervention in "compliers", and their relation to ageing and exposure signature (scores). Many studies have previously identified signatures that that capture epigenetic ageing yet the biological meaning of them remains unclear. It may be beneficial to identify CpG markers that are changed in response to a putative health-promoting intervention specifically and correlate with clinically meaningful changes (e.g. gut microbiome, lung function) in

a well-characterised longitudinal dataset. We may chose to undertake this subsidiary analysis pending the outcome of initial results.

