#### 2.2.3 Subsidiary outcomes or objectives

Subsidiary endpoints include analysis of longer-term changes at month 12 and 18 for participants who provided longer-term samples.

In a subgroup of participants (n=10), we will apply single cell multiomic analysis for RNA and ATAC-seq to investigate cellular heterogeneity at an early time point (two months

of intervention).

A subgroup of participants will be selected to investigate of which epigenetic sites are (individually) altered with cellular Yamanaka factor-induced reprogramming in samples collected at baseline (M0). In these participants we will investigated if the same or similar sites are significantly altered by the intervention at M6 (within-individual); if consistent regions are found across individuals, these sites may also applied to those individuals that were not included in reprogramming analysis.

Lastly, we may explore potential DNAme biomarkers that change in response to the intervention and are associated with clinically meaningful features (e.g. microbiome, lung function).

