# 3.11 Timing of participant visits

Outcomes will be assessed using samples collected at the following timepoints:

- Baseline, including sports medicine examination and vascular analysis. All baseline measurements should be taken within 10 days of inclusion in the study, where feasible.
- Month 2 (7-10 weeks after inclusion)
- Month 4 (16-19 weeks after inclusion)
- Month 6 (25-28 weeks after inclusion)
- Month 12 (optional; 50-55 weeks after inclusion)
- Month 18 (optional; 75-79 weeks after inclusion)

Given practical limitations including annual leave, participant or staff illness, or other unforeseen circumstances, sample and data collection may be conducted outside these windows at the nearest possible date.

Baseline and regular outcome information will be collected in a trial-specific electronic case report form (eCRF), Askimed, by a member of the hospital or research staff at 2, 4, and 6 months of the study regardless of whether the participant is compliant with the intervention or not, although compliance will be monitored via regular check-ups by the coaches, biological measurements, and during study visitations. There are two optional follow-ups at 12 and 18 months. These will not be analysed with regards to primary endpoint but may inform stability of epigenetic changes for follow-up studies.

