# 6.11 Subsidiary analysis: continuous compliance

Continuous compliance to intervention following the initial 6 months will be evaluate at month 6 and month 12 and reported in a summary table.

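### SAP 5.4.3 and 2.2.3 give different populations for month 12/18 stability, and the responder version in 5.4.3 would show a spurious rebound through regression to the mean

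*SAP*

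**What the plan says.** The SAP describes the month 12 and 18 follow-up in four places.

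- Section 2.2.3 sets no response condition: "Subsidiary endpoints include analysis of longer-term changes at month 12 and 18 for participants who provided longer-term samples".
- Section 3.11 offers both visits as optional, again without a response condition, and says of them: "These will not be analysed with regards to primary endpoint but may inform stability of epigenetic changes for follow-up studies".
- Section 5.4.3 first says that optional samples are collected at both visits, then adds that they may be collected to "evaluate long-term stability of changes in those participants that showed epigenetic and other biological changes in response to the intervention". Of the two evaluations listed under that sentence, the one on markers is "variability in epigenetic and other health markers evaluated in primary and secondary endpoints at month 6 and month 12 and/or month 18". The only selection problem it mentions is that "individuals that were highly compliant to begin with may be more likely to return for optional follow ups".
- Section 6.11 covers compliance only: "Continuous compliance to intervention following the initial 6 months will be evaluate at month 6 and month 12".

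Section 5.4.3 does not say which score, direction or size of change makes a participant one who changed. Section 6 and the table in 6.16 contain no method for month 12/18 marker stability. The subsidiary rows are continuous compliance, single-cell sequencing, reprogramming and biomarkers of intervention. The longitudinal models at the start of section 6 use baseline and months 2, 4 and 6.

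**The concern.** Sections 2.2.3 and 5.4.3 define two populations for one objective, and the second is selected on the outcome. A woman is more likely to count as changed if her baseline value happened to be high or her month 6 value happened to be low. The month 6 part of that chance deviation does not recur at month 12, so her score appears to drift back even when nothing has been lost. The baseline part stays in every later comparison with baseline, so any change reported that way looks larger than it is.

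The caveat about compliant women returning more often concerns who comes back. It does not address selection on the measured change. The study has no separate control group against which drift could be judged. What is at stake is the answer to whether changes persist after the programme, which the SAP says may inform follow-up studies.

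**Working it through.** **Inputs from SAP 3.6.** n = 60, difference 0.2, SD 0.44, significance level 0.05 (sidedness not stated; two-sided assumed), power 0.94. The same section says there are no preliminary longitudinal data on the scores.

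**Step 1: what the 0.44 represents.** For a paired comparison by normal approximation, 0.2 / (0.44/√60) = 0.2 / 0.0568 = 3.52, and Φ(3.52 − 1.96) = 0.941. This reproduces the stated 0.94 (a paired t calculation gives 0.934). A two-sample reading with 60 per arm gives 0.70, and a one-sided paired test gives 0.97. So 0.44 behaves as the SD of the month 6 minus baseline change, although the SAP does not call it that.

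**Step 2: model (assumed).** Write the changes from baseline as

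D6 = T + e6 − e0 and D12 = T + e12 − e0,

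where T is a woman's true lasting change with mean μ, and the e terms are independent visit noise. Let s = SD(D6), and let h be the share of s² that comes from stable differences in T. Each visit then has noise variance (1 − h)s²/2. Response is taken as any fall, D6 < 0; the direction follows 5.4.1, which counts reductions as success.

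The selected women's mean month 6 change lies below μ by

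S = s·φ(μ/s) / Φ(−μ/s).

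Because Cov(D12 − D6, D6) = −(1 − h)s²/2 and Cov(D12, D6) = (1 + h)s²/2, the selected women have:

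- month 6 minus baseline = μ − S
- month 12 minus baseline = μ − S(1 + h)/2
- false rebound, month 12 minus month 6 = S(1 − h)/2

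Their true mean change is μ − hS, so month 12 minus baseline overstates it by S(1 − h)/2, the same amount as the false rebound.

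**Step 3: results with s = 0.44.**

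For μ = 0, S = 0.44 × √(2/π) = 0.351. For μ = −0.20, S = 0.44 × 0.3598/0.6753 = 0.234.

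| True mean change | Stable share h | Month 6 − baseline | Month 12 − baseline | False rebound |
|---|---|---|---|---|
| 0 | 0 | −0.351 | −0.176 | +0.176 |
| 0 | 0.25 | −0.351 | −0.219 | +0.132 |
| 0 | 0.5 | −0.351 | −0.263 | +0.088 |
| −0.20, sustained | 0 | −0.434 | −0.317 | +0.117 |
| −0.20, sustained | 0.5 | −0.434 | −0.376 | +0.059 |

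A simulation of 2,000,000 women per scenario agrees to within 0.001. In row 4 nothing was lost, yet 0.117/0.434 = 27% of the month 6 change appears to be.

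**Step 4: other assumptions.**

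- If 0.44 is the single-visit SD with between-visit correlation r, then s = 0.44√(2(1 − r)). For r = 0.5, 0.7 and 0.9 with no effect, the false rebound is 0.18, 0.14 and 0.08.
- If response requires a fall of at least 0.2, with no effect and h = 0, the false rebound is 0.24.
- With no effect, h = 0, 60 women before selection on any fall, and a paired t test (not specified in the SAP for these visits), a significant false rebound occurs in 63% of 20,000 simulated trials. With 48 women (20% dropout) it occurs in 53%.

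**Step 5: no selection.** Using all women, the expected false rebound is 0 in every scenario above, and the false-rebound error rate is about 2.4% against a nominal 2.5% in that direction.

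**The case against.** The best defence is that the SAP never commits to a responder-only analysis. Section 5.4.3 says samples may be collected, its preceding sentence is unrestricted, and 2.2.3 and 3.11 set no response condition. The phrase about women who changed can be read as stating a purpose, since stability matters only where something changed. Section 3.8 withholds key results while the study is in progress, and 3.10 analyses month 6 collectively per sub-study, so inviting women back by epigenetic response would be hard. No responder-restricted analysis appears in section 6 or the summary table.

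Most of this stands. A reader might infer that the SAP has decided to judge long-term stability in responders; the text does not support that. What remains is that two wordings conflict, nothing later resolves them, and selection at assay or analysis stage is open.

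A reader might also infer that a false lasting benefit follows directly from 5.4.3. It does not: the marker evaluation there names months 6, 12 and 18, not baseline. That artefact arises only if change from baseline is reported too. Nor would a responder subset by itself establish an effect, because the primary ITT comparison uses all participants.

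Finally, the responder rule and noise model are assumptions, and a noise-only change is the extreme case. This objection stands for the size of the bias. It does not remove the direction, which holds for selection on a fall whenever there is independent visit-to-visit noise.

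**Conclusion.** The point holds as an unresolved conflict between 5.4.3 and 2.2.3 in which one of the two versions is biased. Following 5.4.3 would produce a spurious rebound from month 6 to month 12 or 18 and, if change from baseline is also shown, an overstated lasting change.

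The size cannot be derived from the SAP. As illustrations, the false rebound is about 0.18 with no effect and about 0.12 with a sustained −0.20, both with noise-only variation in change. It is about 0.09 with no mean effect if half the change variance is stable, and about 0.08 if 0.44 is a single-visit SD with between-visit correlation 0.9. The design difference is 0.2, so even the lower figures are not negligible.

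The importance is moderate: the follow-up is optional, the objective is subsidiary and the study describes itself as predominantly exploratory. The SAP says these data may inform follow-up studies, which is weaker than saying that they will.

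The timepoints in 6.11 are a separate editorial slip. Month 6 is the end of the intervention, so it is not a post-intervention assessment, and month 18 is left out although 2.2.3, 3.11 and 5.4.3 all provide for it. This lends no support to the regression-to-the-mean argument.

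**What to change.** - **5.4.3:** bring it into line with 2.2.3. State that month 12 and 18 samples are sought from, and analysed in, all returning participants irrespective of their month 6 change.
- **Section 6 and table 6.16:** add the method. Estimate month 12 and 18 means relative to baseline and to month 6 in a longitudinal model that includes all participants' baseline to month 6 data, including women who did not return.
- **Responder displays:** if shown, define response beforehand, label the display descriptive and attach a regression-to-the-mean caveat.
- **6.11:** give the post-intervention compliance timepoints as month 12 and month 18.

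The cost is SAP wording. If the assay budget is fixed, some later arrays will be spent on women without a month 6 change.

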# 6 Analysis

Analyses will be conducted and reported separately per sub-study (i.e. smoking cessation and intermittent fasting) after all samples for the month 6 timepoint have been collected. Key analyses will be performed on the ITT population. A per-protocol analysis will be conducted if sufficient individuals are available with above 80% compliance (n=30), or alternatively and additionally a subgroup analyses split by median compliance score (above and beyond, respectively). Descriptive statistics of dynamics over 6 months without an intervention will be reported and if sufficient individuals are present per study arm (n  $\geq 10$ ) that did not adhere, these may be used as a nested control group; although this number is small, it could be informative for dynamic changes without intervention.

The longitudinal manner of data collection enables baseline-controlled pairwise comparison (paired t or Wilcoxon test) for each participant at baseline and after 6 months; linear mixed effects-models may also be employed. Longitudinal dynamics and repeated measurements per participant, evaluating data from baseline, 2, 4, and 6 months, will be assessed using linear (or non-linear) mixed-effects models to account for inter-individual heterogeneity and differences in response (random intercept and slopes, if appropriate). In the intermittent fasting group, cross-sectional analyses may be used to compare effects for use with and without ketogenic supplement. Change from baseline may be reported in a descriptive manner.

Methylation data will be adjusted for sample cell type composition which is known to influence methylation levels. Many of the assessed factors are influenced by age. Dependence on other, non-intervention related covariates will be investigated during the exploratory data visualisation and assessment, and factors may be associated as covariates in mixed-effects models if necessary.

If a number of participants does not adhere to the intervention but continues to provide samples and the assumption of common support holds, we may be able to explore the average treatment effect (ATE) and causal average treatment effect (CATE) using causal inference (g methods) via covariate adjustment for selected secondary outcomes (in particular longitudinal DNA methylation analyses).

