#### 2. Dietary intervention (n = 120)

One-hundred and twenty women without significant prior medical history with a body mass index (BMI) between 25 and 35 will be recruited and aided to conduct 16:8 intermittent fasting (16 h fasting, 8 h window for food consumption each day). The window during which food can be consumed can be freely chosen by each participant Participants will be randomly allocated one of the following groups using age- and BMI-stratified block randomisation:

• Intermittent fasting (n = 60)

Intermittent fasting has been shown to convey a series of metabolic and health benefits, promoting longevity and reducing tumour incidence in animal models. Recent human studies suggest similar benefits in humans. We aim to assess whether intermittent fasting can improve a variety of health parameters.

• Intermittent fasting with ketogenic supplement (n = 60)Intermittent fasting may mediate its benefits via timing of feeding/circadian rhythms, caloric restriction, and/or, in part, by promoting nutritional ketosis via the absence of carbohydrates; promotion of ketosis has been shown to induce longevity in mice. Ketogenic supplements are already commonly used in dietary therapy for pediatric epilepsy, but have not been routinely used in other settings. We aim to assess whether ketogenic supplements may boost ketosis and further enhance the health benefits of intermittent fasting.

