#### 3.5 Randomisation

Eligible participants in the dietary intervention group will be randomised to one of the two interventions using a secure Excel sheet developed by the statistician. The randomisation strategy is menopause- and BMI-stratified block randomisation in blocks of 4. Participants within each block will be allocated to a treatment 1:1. Users (clinicians) will provide menopausal status and BMI group and treatment allocation is then provided. The allocated treatment arm is recorded in the eCRF (Askimed).

No randomisation will be conducted in the smoking cessation sub-study.

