## 3.6 Sample size

The sample size of n = 60 per group is based on an initial estimation of the potential clinically relevant effect and variance as part of the preceding FORECEE project: a total of 60 participants are required to detect a difference of 0.2 in DNA methylation indices (e.g. WID-BC index), assuming a standard deviation of 0.44, at a statistical power of 0.94 and a significance level of 0.05. There are no preliminary data for longitudinal changes in the WID scores, thereby TirolGESUND acts as a pilot study to define effect sizes and variance for larger prospective studies in the future.

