#### 6.5.3 Secondary endpoint reporting

Paired analysis (ITT) will be conducted for baseline and month 6 measurements. As with the primary endpoint, PP or above/below median compliance score subgroup analysis may be additionally constructed. Linear-mixed effects models will be constructed to explore heterogeneity in responses among participants and leverage the strength of our longitudinal data. In addition, descriptive statistics relating to change to baseline can be reported. The following outcomes will be assessed:

- body mass index  $(kg/m^2)$ , diet arm of the study
- fat-free body mass (%), diet arm of the study
- current smoking ("yes" or "no", binary response, can be analysed using a generalised estimation equation or generalised linear mixed model with a log link function)
- vascular health parameters
  - pulse wave velocity (mm/s)
  - intima-media thickness (mm)
  - plaque score
- physical activity
  - international physical activity questionnaire (IPAQ) score
  - average daily steps per week
  - active minutes per week
- abdominal fat composition, diet arm of the study
  - visceral fat (mm)
  - subcutaneous fat (mm)
- heart rate variability (ms)
- resting heart rate (beats per minute)
- sleep quality score (fitness tracker, average score per week)
- subgroup in diet arm of the study:  $\beta$ -hydroxybutyrate levels

- pulmonary health, including FEV1, FVC, and FEV1/FVC
- ergonometry functional values

Data will be reported using spaghetti plots (visualising individual values) and/or tables of mean and standard deviations. In the diet arm, changes in body mass index, fat-free body mass, and abdominal fat composition may also be compared between groups (with and without ketogenic supplement) using Wilcoxon testing of delta change, or via inclusion of ketogenic supplement covariate in linear mixed models.

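### The supplement comparison, the trial's only randomised contrast, has no fixed analysis tied to the baseline value or the randomisation strata, and the strata are stated in two ways

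*SAP*

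**What the plan says.** Section 3.1 sets up the diet sub-study as a randomised trial of fasting with and without supplement, 60 women per arm. Section 3.5 confirms that the smoking sub-study is not randomised.

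The arm comparison appears in four places:

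- Section 5.4.1 lists it among the subgroup analyses of the primary objective: "investigation of difference between individuals who received ketogenic supplement and those that did not at 6 months".
- Section 6: "In the intermittent fasting group, cross-sectional analyses may be used to compare effects for use with and without ketogenic supplement". The next sentence there allows change from baseline to be reported descriptively.
- Section 6.4.3 says that the two randomised arms may be compared on the primary endpoint, without naming a method. The table in section 6.16 repeats the comparison as a note.
- Section 6.5.3, for BMI, fat-free mass and abdominal fat, offers "Wilcoxon testing of delta change, or via inclusion of ketogenic supplement covariate in linear mixed models".

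The null hypothesis in section 3.7 concerns baseline against month 6 only. There is none for the arms.

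The strata are given twice. Section 3.1 has participants allocated "using age- and BMI-stratified block randomisation". Section 3.5 says: "The randomisation strategy is menopause- and BMI-stratified block randomisation in blocks of 4".

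**The concern.** The rest of the trial is a before-after comparison without a control group, so it cannot separate an intervention effect from time trends or from selection. The supplement contrast can. It is also the contrast with the loosest analysis: several options, mostly worded as permissions, and none stated to use the baseline score as a covariate or the factors that the allocation was stratified on.

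Two things are at stake. A comparison of month-6 values alone discards a baseline score that every woman is due to provide, and so loses precision. Open options also let the analysis be chosen after the data are seen. The conflict over strata adds a practical obstacle: nobody can adjust for the stratification factors, or report the randomisation correctly, until it is known whether the second factor was age or menopausal status.

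**Working it through.** **Inputs.** From section 3.6: "a total of 60 participants are required to detect a difference of 0.2 in DNA methylation indices", "assuming a standard deviation of 0.44, at a statistical power of 0.94 and a significance level of 0.05". From section 3.1: 60 per arm. From section 5.4.2: dropout of 15-20%. The correlation ρ between baseline and month 6 is not given ("There are no preliminary data for longitudinal changes in the WID scores"), so I assume 0.3, 0.5 and 0.7. Tests are two-sided, which the SAP does not state but which reproduces its figure.

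**The SAP's own figure.** As a paired within-group test: Φ(0.2/0.44 × √60 − 1.96) = Φ(3.52 − 1.96) = 0.941. This agrees with the stated 0.94. It is the power of the before-after test in one group, not of the arm comparison.

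**Arm comparison.** With n per arm, the non-centrality is 0.2 / (SD × √(2/n)), referred to a t distribution with 2n − 2 degrees of freedom. Let s be the SD at one visit, equal at both visits:

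- month 6 only: SD = s
- change score: SD = s√(2(1 − ρ))
- month 6 adjusted for baseline (ANCOVA): SD = s√(1 − ρ²)

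For month 6 only with s = 0.44 and n = 60, the non-centrality is 0.2 / (0.44 × √(2/60)) = 2.49 and the power is 0.695.

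Reading 0.44 as the single-visit SD, 60 per arm:

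| ρ | SD change | SD ANCOVA | Power, month 6 | Power, change | Power, ANCOVA |
|---|---|---|---|---|---|
| 0.3 | 0.521 | 0.420 | 0.695 | 0.551 | 0.735 |
| 0.5 | 0.440 | 0.381 | 0.695 | 0.695 | 0.814 |
| 0.7 | 0.341 | 0.314 | 0.695 | 0.890 | 0.933 |

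With 20% dropout (60 × 0.8 = 48 per arm) and ρ = 0.5, the three powers are 0.60, 0.60 and 0.72.

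Reading 0.44 as the SD of change, which is the role it plays in the paired calculation, s = 0.44/√(2(1 − ρ)). At ρ = 0.7, s = 0.568 and the powers are 0.48 (month 6), 0.70 (change) and 0.76 (ANCOVA).

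The normal approximation gives values within 0.01 of all of these.

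**A comparison that needs neither 0.2 nor 0.44.** The ANCOVA variance is (1 − ρ²) times that of month 6 only, and (1 + ρ)/2 times that of the change score. At ρ = 0.5 both ratios are 0.75. At ρ = 0.7 they are 0.51 and 0.85. Neither exceeds 1, so ANCOVA is never less precise apart from one degree of freedom, for WID scores or body composition alike.

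**The mixed-model option.** Section 6 takes baseline, 2, 4 and 6 months as responses. Suppose the supplement covariate is a single main effect, with a random intercept and complete data. It then estimates the average arm difference over the visits, including baseline, where the expected difference is zero:

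- effect constant from month 2: (0 + 1 + 1 + 1)/4 = 0.75 of the month-6 effect
- effect growing linearly to month 6: (0 + 1/3 + 2/3 + 1)/4 = 0.50

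A month-6 difference of 0.2 would be estimated as 0.15 or 0.10.

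**Strata.** Age with BMI (section 3.1) and menopausal status with BMI (section 3.5) are different schemes. Section 3.5 adds that clinicians enter menopausal status and BMI group to obtain the allocation, which leaves no role for age.

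**The case against.** The strongest reply is that the study calls itself exploratory, warns in section 2.1 that not every measure may be adequately powered, and makes most of these comparisons optional. Month-6 and change-score comparisons are both unbiased under randomisation. Preferring ANCOVA is therefore a matter of efficiency, and at ρ = 0.3 on the single-visit reading it gains only 4 points over month 6 alone (0.735 against 0.695). That stands, and it limits the severity. It does not explain leaving the analysis open when section 1 says that the reported results will follow this strategy.

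A reader might infer more than the document supports:

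- **That the plan ignores baseline altogether.** Only the month-6 comparison does. A change score uses baseline by subtraction, and the mixed model uses it as a response.
- **That the arms are to be compared as treated**, because section 5.4.1 speaks of women who received the supplement. Sections 6.4.3 and 6.16 refer to the randomised arms, and sections 5.2 and 6 put the primary and key analyses on the ITT population. The word is loose, no more.
- **That the plan dilutes the supplement effect.** No model without an arm-by-visit term is written out for this comparison. It is one reading of the word covariate. It concerns the body-composition outcomes of section 6.5.3, not the WID scores. Even then, with a constant effect and ρ = 0.3, its power is 0.77 against 0.74 for ANCOVA, although its estimate is still shrunk.
- **That stratification-type factors are absent from every model.** Equation 1 in section 6.4.4 contains BMI and baseline age. It has no supplement term and no menopausal status, and it is offered as an example that may be changed.

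**Conclusion.** The point holds in this form: the only randomised contrast has no single specified analysis, none of the options named for it is tied to the baseline value as a covariate or to the randomisation strata, and the strata themselves are contradictory. The last part needs no assumption.

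ANCOVA is ahead of both simpler analyses at each correlation shown and under either reading of 0.44. The size of the gain is conditional. Over month 6 alone it runs from 4 points (ρ = 0.3) to 24 points (ρ = 0.7) on the single-visit reading, and is 28 points at ρ = 0.7 if 0.44 is the SD of change. Over the change score it runs from 18 points (ρ = 0.3) down to 4 points (ρ = 0.7) on the single-visit reading. These figures use WID planning values; the change-score option is written for body-composition outcomes, to which only the variance ratios carry over. The loss of 25% to 50% of the effect in the mixed model is a risk that the wording leaves open, not a stated plan.

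This should be changed before analysis. It does not invalidate the before-after primary analysis.

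**What to change.** 1. State one analysis for all supplement comparisons, by randomised arm: month-6 value on arm, adjusted for the baseline value of the same outcome and for the stratification factors actually used. For outcomes measured at several visits, an equivalent choice is a mixed model with visit and arm-by-visit terms and a common baseline mean, reporting the month-6 contrast.
2. Replace the alternatives in sections 5.4.1, 6, 6.4.3 and 6.5.3 with a reference to that statement, and describe the groups by allocation.
3. Add a between-arm null hypothesis at month 6 to section 3.7.
4. Check the allocation sheet and make sections 3.1 and 3.5 name the same factors.

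The cost is SAP wording. Baseline outcome values, age, BMI and menopausal status are already collected.
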